# 4.4.5 Exploratory Endpoint Analysis Methods

# 4.4.6 Sensitivity Analysis of Efficacy Endpoints

Sensitivity analyses of the primary endpoint will be conducted to better assess the impact of intercurrent events on the efficacy conclusions. The intercurrent events of interest include receipt of prohibited and/or rescue medications while on study and early withdrawal of study drug. The treatment policy strategy will be used for the primary estimand.

The while on treatment strategy will be used as a sensitivity analysis to further explore the intercurrent event of prohibited and/or rescue medication usage. The difference in means between treatment groups in the weekly WI-NRS score at the last visit prior to receipt of prohibited and/or rescue medications (or the last derived weekly WI-NRS score, for those who never require prohibited and/or rescue medication) will be presented during the Double-Blind Treatment Period. For those subjects that receive a prohibited and/or rescue medication, any WI-NRS scores reported after the receipt of medication will be excluded from the analysis.

Determination of intercurrent events based on use of a prohibited and/or rescue medication will be based on review of the Concomitant Medication eCRF. Before study unblinding, the sponsor will review all reported concomitant medications, including onstudy changes to background medications, to determine which qualify as an intercurrent event for prohibited or rescue medication usage. This external assessment will be documented in the study files and integrated into the sensitivity analysis.

The analysis of the primary efficacy endpoint will be analyzed for the Full Analysis Set using multiple imputations (MI) assuming data missing at Week 6 to be missing at random (MAR) (Section 4.4.7.2), and for the Per Protocol Set using observed data.

Treatment group comparisons will use the methodology described in Section 4.4.3 for sensitivity analysis of the primary endpoint.

Secondary and PD endpoint analyses during the Double-Blind Treatment Period will be repeated for the Per Protocol Set as supportive analyses.

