# 4.4.3 Primary Efficacy Endpoint Analysis Methods

The primary estimand is the difference in means between treatment groups in the weekly WI-NRS score at Week 6 for all subjects in the Full Analysis Set. The treatment policy strategy for addressing intercurrent events will be used for the primary estimand; data collected following use of prohibited and/or rescue medications or for subjects who prematurely discontinue from study drug use will be reported in the analysis. The WI-NRS data will be analyzed using a mixed effects model for repeated measures (MMRM) based on the data from weekly scores up to Visit 6 (Week 6) in the Double-Blind Treatment Period. The model will include treatment, type of cholestatic disease (PBC, PSC), week, and treatment by week interaction as fixed effects, and the baseline WI-NRS weekly score as a covariate. The unstructured covariance model will be used. In the event the computational algorithm fails to converge, the following structures will executed: heterogeneous Toeplitz, Toeplitz, heterogeneous Autoregressive [AR(1)], AR(1), heterogeneous compound symmetry (CS), and CS. The covariance structure converging to the best fit, as determined by Akaike's information criterion (AIC), will be used. The Kenward-Roger approximation will be used to calculate the denominator degrees of freedom for the test of fixed effects. The null hypothesis to be tested is that there is no difference between EP547 and Placebo:

$$H_0$$
:  $\mu_A = \mu_B$ ;

Where  $\mu_A$  and  $\mu_B$  represent the mean values for EP547 and Placebo, respectively. The alternate hypothesis to be tested is that the treatment group means differ:

$$H_1$$
:  $\mu_A \neq \mu_B$ ;

Testing of the hypothesis is 2-sided at a 5% type I error level. Estimates of least-square (LS) means, standard error, and 95% CIs will be presented by treatment group. In addition, the LS mean difference (LSMD) of the comparison between EP547 and placebo, the standard error of the difference, and 95% CI of the difference will be presented.

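### SAP 4.4.6 defines the while-on-treatment analysis on each subject's last score before rescue, but sends the comparison to the Week 6 MMRM, which estimates a different quantity

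*SAP*

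**What the plan says.** SAP 4.4.6 names the strategy: "The while on treatment strategy will be used as a sensitivity analysis to further explore the intercurrent event of prohibited and/or rescue medication usage". It defines the quantity as "The difference in means between treatment groups in the weekly WI-NRS score at the last visit prior to receipt of prohibited and/or rescue medications", with an alternative for everyone else: "or the last derived weekly WI-NRS score, for those who never require prohibited and/or rescue medication". For subjects who do take such medication, "any WI-NRS scores reported after the receipt of medication will be excluded from the analysis".

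After a paragraph on the multiple-imputation and Per Protocol analyses, the section closes the topic with one sentence on method: "Treatment group comparisons will use the methodology described in Section 4.4.3 for sensitivity analysis of the primary endpoint".

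SAP 4.4.3 is an MMRM on weekly scores up to Week 6. Its terms are given as follows: "The model will include treatment, type of cholestatic disease (PBC, PSC), week, and treatment by week interaction as fixed effects", with baseline WI-NRS as covariate and an unstructured covariance tried first. Its target is the difference in means at Week 6. Protocol 14.8.3 states that this analysis uses observed data without imputation under missing at random (MAR). ANCOVA appears in SAP 4.4.3 only as something that may be explored post hoc if the MMRM fails to converge.

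**The concern.** The two instructions in SAP 4.4.6 do not fit together. The definition calls for one number per subject, taken at a week that differs between subjects. The method needs a series of weekly scores per subject and reports a contrast at a fixed week. A programmer has to drop one of the two, and the SAP does not say which.

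The natural shortcut is to delete post-rescue scores and rerun the MMRM. That gives a legitimate estimate of a different estimand. The clinical study report could then show a while-on-treatment result that is really a no-rescue prediction at Week 6. The SAP's introduction says the plan is detailed so that such choices are not made post hoc. Here the estimand of a named sensitivity analysis would be settled at the programming stage.

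**Working it through.** **Plan's own figure.** SAP 4.6: 26 / (1 - 0.10) = 28.9, so 29 per group and 58 in total. This reproduces, and it does not depend on the present point.

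**The two instructions side by side.**

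| | Definition in SAP 4.4.6 | Method in SAP 4.4.3 |
|---|---|---|
| Records per subject | One | Up to six weekly scores |
| Time point | Varies by subject | Week 6 |
| What a rescued subject contributes | The last score before rescue, as observed | Scores before rescue, from which Week 6 is implicitly predicted |

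**If the MMRM is applied to the defined variable.** With one record per subject there are no within-subject pairs of weeks, so an unstructured covariance cannot be estimated. The treatment-by-week term would compare only subjects whose last score fell in the same week. The model does not return the stated difference in means.

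**If the MMRM is applied to weekly data truncated at rescue.** Under MAR, the Week 6 mean for a rescued subject is predicted from that subject's earlier scores and from unrescued subjects with similar histories. The contrast is the Week 6 difference had rescue not occurred. Scores after study drug is stopped without rescue stay in, so the estimand is hypothetical for rescue and treatment policy for drug discontinuation.

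**Numerical check.** All of these inputs are assumptions:
- 200,000 subjects per arm, mean baseline 6.5, SD 2.0 at each week, correlation 0.7 between weeks, scores not limited to 0-10.
- Linear change to Week 6 of -1.5 on placebo and -3.5 on EP547, a difference of -2.00. The design difference is redacted in the current text.
- Rescue possible after each of Weeks 1 to 5, with a logistic hazard depending on the current weekly score and calibrated to the total rates below. Rescue depends only on observed scores, so MAR holds.

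The MMRM column is the large-sample likelihood estimate at Week 6 from the truncated data. The next column is the mean change at the last qualifying score, EP547 minus placebo.

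| Rescue, placebo / EP547 | Truncated MMRM | Last-score difference | Gap |
|---|---|---|---|
| 0% / 0% | -2.00 | -2.00 | 0 |
| 10% / 10% | -2.00 | -1.87 | +0.13 |
| 20% / 20% | -2.00 | -1.75 | +0.25 |
| 20% / 5% | -2.00 | -2.14 | -0.14 |
| 30% / 10% | -2.00 | -2.15 | -0.15 |
| 5% / 20% | -2.00 | -1.53 | +0.47 |
| 10% / 30% | -2.00 | -1.33 | +0.67 |

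Example by arm at 20% / 5%: last-score change is -1.22 on placebo and -3.36 on EP547; -3.36 - (-1.22) = -2.14.

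With no true difference at Week 6 (both arms -1.5), the MMRM gives 0.00. The last-score difference is -0.21 at 20% / 5% and -0.27 at 30% / 10%.

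**Why the sign varies.** Suppose first that rescue is unrelated to the score. Let c be an arm's Week 6 change, p its rescue rate and m the mean week of the last score among those rescued, with subscript P for placebo and A for EP547. Then gap = cP pP (1 - mP/6) - cA pA (1 - mA/6). With m equal in both arms the sign follows cP pP - cA pA:
- at 10% / 10%: -0.15 + 0.35 = +0.20, so the difference shrinks;
- at 20% / 5%: -0.30 + 0.175 = -0.125, so it grows.

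Rescue driven by high scores adds a second component, because the last score is then above the subject's expected path. With fast onset the first component disappears and only this selection remains.

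**Scale.** With SD 2.5 and 26 per group (SAP 4.6), the standard error of a difference is 2.5 x sqrt(2/26) = 0.69. Gaps of 0.13 to 0.67 are 19% to 97% of one standard error. In the four non-zero scenarios where placebo rescue is at least as frequent as EP547 rescue, gaps of 0.13 to 0.25 are 19% to 36%.

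**The case against.** **The method sentence may be meant only for the paragraph before it**, on multiple imputation and Per Protocol. This is possible, but the sentence refers to sensitivity analysis of the primary endpoint in general. On the narrow reading the while-on-treatment analysis has no stated model at all, so the section still needs an edit.

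**ANCOVA may be understood.** SAP 4.4.7.1 speaks of MMRM or ANCOVA according to endpoint. Protocol 14.8.2 uses ANCOVA for continuous secondary and exploratory endpoints not collected at several post-baseline visits. Both make ANCOVA a natural guess. Neither assigns it here, and SAP 4.4.3 reserves it for non-convergence of the primary model. What stands is that the mislabelled result is the outcome of the text as worded, not a certainty about what will be programmed.

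**Three stronger readings are tempting and are not supported.**
- A reader might infer that no other analysis responds to rescue. The primary endpoint is repeated in the Per Protocol Set, and SAP 4.2 gives qualifying rescue use as a ground for exclusion. That drops whole subjects along with other deviations, so it does not isolate rescue, but it does respond to it.
- A reader might infer that early stopping of study drug is not examined. The multiple-imputation analysis in SAP 4.4.7.2 has a separate step for data missing after discontinuation of randomized treatment. It assumes MAR and keeps observed scores, so coverage is partial.
- A reader might fault the analysis for keeping scores after the last dose. SAP 4.4.6 limits it to prohibited and rescue medication and leaves drug discontinuation under treatment policy. A last-dose cut-off would be a different analysis, not a correction.

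**The size is uncertain and the consequence limited.** Both are true. Stable itch regimens and limits on new prescriptions may keep rescue rates low over six weeks.

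**Conclusion.** The inconsistency is real and can be seen by reading SAP 4.4.6 against 4.4.3. The defined quantity and the assigned model are different estimands. They coincide in the simulation when nobody is rescued and differed in every scenario with rescue. That the truncated MMRM targets the no-rescue Week 6 difference follows from the MAR assumption and does not depend on a particular rescue rate.

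The gap of 0.13 to 0.67 points on an assumed 2-point effect is illustrative. It rests on assumed rescue rates, linear onset, SD, correlation and hazard, and both its size and its sign change with them.

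This concerns one sensitivity analysis. The primary estimand, test, alpha and sample size are untouched. It should be corrected before unblinding, but it does not threaten the trial's main conclusion.

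**What to change.** In SAP 4.4.6:
- State that the last qualifying weekly WI-NRS score, as change from baseline, is analysed by ANCOVA with treatment, disease type (PBC, PSC) and baseline WI-NRS.
- Restrict the reference to Section 4.4.3 to the multiple-imputation and Per Protocol analyses.
- If the MMRM on data truncated at rescue is also wanted, list it separately and label it a hypothetical-strategy analysis for rescue.

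Truncating at the last dose of study drug is an optional further analysis and not part of this correction.

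The cost is about two sentences in the SAP and one ANCOVA table. No new data are needed, because SAP 4.4.6 already provides for identifying the qualifying medications before unblinding.

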
Synopsis (Sample Size Considerations) 14.4. Sample Size Considerations
	
Assuming a standard deviation of 2.5 points, a sample size of 26 subjects per treatment group provides approximately 80% power to detect a difference of 2.0 points between EP547 and placebo with respect to the change in weekly mean of the daily WI-NRS score based on a 2-sided, 2-sample comparison of means at the 5% significance level. With an anticipated early withdrawal rate of approximately 5%, the planned enrollment of 34 subjects per treatment group will ensure that at least 26 subjects complete the 6 weeks of double-blind treatment.
	
Assuming a standard deviation of 2.5 points, a sample size of 26 subjects per treatment group provides approximately [REDACTED] % power to detect a [REDACTED] EP547 and placebo with respect to the change in weekly mean of the daily WI-NRS score based on a 2-sided, 2-sample comparison of means at the 5% significance level. With an anticipated early withdrawal rate of approximately 10%, the planned enrollment of 29 subjects per treatment group will ensure that at least 26 subjects complete the 6 weeks of double-blind treatment.
	
Refinements to the statistical assumptions allowed for a smaller sample size for analysis of the primary endpoint.
																																																								

5.3. EP547 and Study Rationale
	
Study EP-547-201 is designed to evaluate the effects of EP547 on reducing the sensation of pruritus over 6 weeks in approximately 62 subjects diagnosed with cholestatic pruritus due to PBC or PSC.
	
Study EP-547-201 is designed to evaluate the effects of EP547 on reducing the sensation of pruritus over 6 weeks in approximately 58 subjects diagnosed with cholestatic pruritus due to PBC or PSC.
	
Refinements to the statistical assumptions allowed for a smaller sample size for analysis of the primary endpoint.
																																																								

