# 4.6 Determination of Sample Size

Assuming a standard deviation of 2.5 points, a sample size of 26 subjects per treatment group provides approximately % power to detect a EP547 and placebo with respect to the change in weekly mean of the daily WI-NRS score based on a 2-sided, 2-sample comparison of means at the 5% significance level. With an anticipated early withdrawal rate of approximately 10%, the planned enrollment of 29 subjects per treatment group will ensure that at least 26 subjects complete the 6 weeks of double-blind treatment.

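### SAP 4.4.6 defines the while-on-treatment analysis by each subject's last weekly WI-NRS score before rescue, but assigns it to the Week 6 MMRM, which estimates a hypothetical no-rescue difference

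*SAP*

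**What the plan says.** SAP 4.4.6 names a while-on-treatment strategy to explore prohibited and rescue medication, and defines the quantity as "The difference in means between treatment groups in the weekly WI-NRS score at the last visit prior to receipt of prohibited and/or rescue medications". Subjects who never take such medication contribute their last derived weekly score, whichever week that is. For those who do take it, "any WI-NRS scores reported after the receipt of medication will be excluded from the analysis".

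The section goes on to the multiple-imputation (MI) and Per Protocol analyses of the primary endpoint. It closes the topic with "Treatment group comparisons will use the methodology described in Section 4.4.3 for sensitivity analysis of the primary endpoint". No analysis is exempted.

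SAP 4.4.3 sets the primary estimand at Week 6 and fits an MMRM to the weekly scores up to that visit: "The model will include treatment, type of cholestatic disease (PBC, PSC), week, and treatment by week interaction as fixed effects", with baseline WI-NRS as covariate, an unstructured covariance and Kenward-Roger degrees of freedom. "Testing of the hypothesis is 2-sided at a 5% type I error level". The only single-endpoint model in 4.4.3 is an ANCOVA that may be explored post hoc if the MMRM does not converge.

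**The concern.** The defined quantity is a comparison of one number per subject, taken at different weeks for different subjects. The assigned method compares arms at one fixed week and fills the gap for subjects without a Week 6 score through the modelled correlations. These are different estimands, and the SAP gives the first one's name to the second one's result.

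The analysis exists to show whether rescue use alters the efficacy conclusion. If its estimate differs from the primary one, the reader needs to know whether that reflects itch while subjects were free of rescue, or a projection to a Week 6 without rescue. As written, the first label would be attached to the second quantity.

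**Working it through.** **1. The plan's own figures.** SAP 4.6: "Assuming a standard deviation of 2.5 points, a sample size of 26 subjects per treatment group provides approximately" a redacted power; "With an anticipated early withdrawal rate of approximately 10%, the planned enrollment of 29 subjects per treatment group". Check: 26 / (1 − 0.10) = 28.9, rounded up to 29 per arm, 58 in total. This reproduces. Power and difference are redacted in the current text. The superseded column of the Protocol's Amendment 2.0 log reads "provides approximately 80% power to detect a difference of 2.0 points between EP547 and placebo". With SD 2.5 and 26 per arm, the normal approximation gives 2.0 / (2.5 × √(2/26)) − 1.96 = 0.92, or 82.2% power. The t-test gives 80.7%. The 2.0-point effect is used below only as an assumption. The point itself rests on no stated figure.

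**2. Target and method side by side.**

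| | Defined in 4.4.6 | Delivered by 4.4.3 |
|---|---|---|
| Values per subject | one | up to six weekly scores |
| Time point | last score before medication, any week | Week 6 |
| Rescued subject | last pre-medication score, as observed | earlier weeks kept, Week 6 inferred under missing at random |
| Unrescued early dropout | last derived score | projected to Week 6 |

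The MMRM cannot sensibly be fitted to the last scores alone: with one value per subject, no within-subject correlation can be estimated.

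**3. Size of the gap.** Assumptions: six weekly change scores, SD 2.5, between-week correlation 0.7, no-rescue Week 6 difference −2.0, and rescue from Week 2 on, more likely after a high score the week before. Cumulative rescue proportion p is spread as a weekly hazard h = 1 − (1 − p)^(1/5). There were 40,000 subjects per arm, so the standard error of a difference is about 2.5 × √(2/40,000) = 0.018. The Week 6 contrast was obtained by sequential regression under missing at random, a large-sample stand-in for the MMRM. Baseline and disease type were left out.

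| Effect | Rescue, placebo / EP547 | Last score before rescue | Week 6 contrast | Gap |
|---|---|---|---|---|
| Builds linearly | 0 / 0 | −1.98 | −1.98 | 0.00 |
| | 10% / 5% | −2.02 | −2.01 | −0.01 |
| | 30% / 10% | −2.14 | −1.99 | −0.15 |
| | 20% / 20% | −1.78 | −1.99 | +0.21 |
| | 30% / 30% | −1.67 | −1.98 | +0.31 |
| Immediate | 10% / 5% | −2.02 | −1.99 | −0.03 |
| | 30% / 10% | −2.15 | −2.00 | −0.15 |
| | 30% / 30% | −2.01 | −2.01 | 0.00 |

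The Week 6 contrast stays at −1.98 to −2.01 throughout, which is the assumed no-rescue effect. The last-score difference runs from −1.67 to −2.15.

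**4. Hand check of the largest gap.** For 30% in both arms, h = 1 − 0.7^(1/5) = 0.0689. The last score falls in Weeks 1 to 5 with probabilities 0.0689, 0.0641, 0.0597, 0.0556 and 0.0518, and in Week 6 with probability 0.70. The mean last week is 0.857 + 4.20 = 5.06. With the effect proportional to week, the expected difference is −2.0 × 5.06 / 6 = −1.69, in line with the simulated −1.67.

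**The case against.** The strongest defence is that this is a gap in wording. The last-score difference is only to be presented, which could mean descriptively. The sentence pointing to 4.4.3 directly follows the MI and Per Protocol paragraph. SAP 4.4.7.1 allows MMRM or ANCOVA depending on the endpoint, and Protocol 14.8.2 uses ANCOVA for continuous secondary endpoints not measured at several post-baseline visits. These passages make the likely intention easy to guess, but none assigns a model to this analysis. The while-on-treatment analysis is introduced as a sensitivity analysis of the primary endpoint, which is what the 4.4.3 sentence covers. The ANCOVA in 4.4.3 is only a post-hoc option after non-convergence.

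Three stronger readings are tempting but not supported:

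- **That the analysis loses power.** Tests of two different quantities have no common power to lose, and the comparison depends on the assumed onset. In a small simulation with 29 per arm and 300 trials per setting, a constant 1.5-point effect with rescue in 28% (EP547) and 46% (placebo) gave 71% for ANCOVA on the last score and 46% for the MMRM. When the effect instead built linearly to 1.5 points (rescue 37% and 45%), the figures were 35% and 40%. The ANCOVA advantage disappears and, if anything, reverses, since each figure has a standard error of about √(0.4 × 0.6 / 300) = 0.028. The SAP makes no power claim for this analysis.
- **That rescued subjects drop out, leaving an unrescued-only comparison.** The SAP excludes only scores after the medication, so earlier weeks stay in the MMRM.
- **That this is the only planned analysis bearing on rescue.** SAP 4.2 removes subjects with qualifying prohibited or rescue use from the Per Protocol Set, and the primary endpoint is repeated on that set.

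It also stands that the consequence is small when rescue is rare.

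**Conclusion.** Wrong as written, low severity. Taken literally, SAP 4.4.6 yields a hypothetical no-rescue Week 6 difference under a while-on-treatment label. That conclusion follows from the text and needs no simulation.

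The size does rest on assumptions. With a 2.0-point effect, SD 2.5 and correlation 0.7, the gap is about 0 at low rescue rates and reaches about 0.3 points at 30% rescue in both arms with a gradually building effect. It is about 0.15 points in the other direction when placebo subjects are rescued more often (30% against 10%). Neither the rescue rates nor the time course is in the documents, so no single figure or direction can be claimed. The primary treatment-policy analysis and the sample size are unaffected.

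**What to change.** In SAP 4.4.6, before unblinding:

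- Limit the reference to Section 4.4.3 to the MI and Per Protocol analyses.
- For the while-on-treatment analysis, specify an ANCOVA on change from baseline to the last derived weekly WI-NRS score before prohibited or rescue medication (or the last derived weekly score if none). Use treatment and type of cholestatic disease (PBC, PSC) as fixed effects and baseline WI-NRS as covariate. Report LS means, LS mean difference, 95% CI and p-value.
- State how subjects with no post-baseline weekly score before the medication are handled.
- If the MMRM on the truncated data is also kept, label it as a hypothetical (no-rescue) strategy.

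The cost is one or two sentences, plus one for the no-score rule, and one ANCOVA of the form already planned in SAP 4.4.4.1. No new data are needed.
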